16.8.1 Incomplete Start Date

The following rules will be applied to impute the missing numeric fields for an incomplete prior or concomitant medication start date. If the stop date is complete and the imputed start date is after the stop date, the start date will be imputed using the stop date.

Missing month and day

- If the year of the incomplete start date is the same as the year of the first dose of OL IP, the month and day of the first dose of open-label IP will be assigned to the missing fields
- If the year of the incomplete start date is before the year of the first dose of OL IP, *December 31* will be assigned to the missing fields
- If the year of the incomplete start date is after the year of the first dose of OL IP, *January 1* will be assigned to the missing fields

Missing month only

- If only the month is missing, the day will be treated as missing and both the month and the day will be replaced according to the above procedure

Missing day only

- If the month and year of the incomplete start date are the same as the month and year of the first dose of OL IP, the day of the first dose of OL IP will be assigned to the missing day
- If either the year of the incomplete start date is before the year of the date of the first dose of OL IP or if both years are the same but the month of the incomplete start date is before the month of the date of the first dose of OL IP, the last day of the month will be assigned to the missing day.
- If either the year of the incomplete start date is after the year of the date of the first dose of OL IP or if both years are the same but the month of the incomplete start date is after the month of the date of the first dose of OL IP, the first day of the month will be assigned to the missing day

16.8.2 Incomplete Stop Date

The following rules will be applied to impute the missing numeric fields for an incomplete prior or concomitant medication stop date for a patient in the respective safety population (OL Safety Population or DB Safety Population). If the date of the last dose of IP in one of the periods is missing, replace it with the last visit date during the corresponding period in the imputations described below. If the imputed stop date is before the start date (imputed or non-imputed start date), the imputed stop date will be equal to the start date.

Missing month and day

- If the year of the incomplete stop date is the same as the year of the last dose of IP, the month and day of the last dose of IP will be assigned to the missing fields
- If the year of the incomplete stop date is before the year of the last dose of IP, *December 31* will be assigned to the missing fields
- If the year of the incomplete stop date is after the year of the last dose of IP, *January 1* will be assigned to the missing fields

Missing month only

- If only the month is missing, the day will be treated as missing and both the month and the day will be replaced according to the above procedure

Missing day only

- If the month and year of the incomplete stop date are the same as the month and year of the last dose of IP, the day of the last dose of IP will be assigned to the missing day
- If either the year of the incomplete stop date is before the year of the date of the last dose of IP or if both years are the same but the month of the incomplete stop date is before the month of the date of the last dose of IP, the last day of the month will be assigned to the missing day
- If either the year of the incomplete stop date is after the year of the date of the last dose of IP or if both years are the same but the month of the incomplete stop date is after the month of the date of the last dose of IP, the first day of the month will be assigned to the missing day

16.9**CHARACTER VALUES OF CLINICAL LABORATORY
PARAMETERS**

If the reported value of a clinical laboratory parameter cannot be used in a statistical summary table because, for example, a character string is reported for a parameter of the numeric type, a coded value must be appropriately determined for use in the statistical analyses. The actual values, however, as reported in the database will be presented in the data listings.

17.0 CHANGES TO ANALYSES SPECIFIED IN PROTOCOL

In Section 11.1 (Adverse Events), AE summary timeframe was modified to align with AE reporting period specified in the protocol amendment 4 (dated in December 17th, 2019). The new time frame is defined below.

An AE that occurs more than 30 days after the date of the last dose of DB IP or occurs after the last SFU visit (whichever comes last) will not be summarized except for AEs related to reported pregnancies. AEs associated with pregnancies reported in the protocol-required timeframe up to approximately 12 weeks following the last dose of DB IP will be summarized.

The summary of SAEs was modified in Section 11.1. The definition of on-therapy SAE was updated to TESAE, and summary timeframe will align with general AE summary timeframe as specified above.

18.0

COVID-19 RELATED LISTING

A listing of patients with visits impacted by COVID-19 will be provided.

19.0 REFERENCES

National Institutes of Health, National Heart, Lung, and Blood Institute, National High Blood Pressure Education Program. The Seventh Report of the Joint National Committee on Prevention, Detection, Evaluation, and Treatment of High Blood Pressure. NIH Publication No. 04-5230, 2014

20.0**APPENDICES****APPENDIX I SAS CODE FOR PLANNED ANALYSES OF THE PRIMARY EFFICACY VARIABLE**

The primary efficacy analysis for time to relapse include (1) the log-rank test, (2) the Cox proportional hazards model with treatment group as covariate, (3) subgroup analysis. The sample SAS code for these analyses are provided below. Note in the data set adtte (DB ITT population), variables trt02pn and trt02p are for the double-blind treatment group, subgroup is for subgroups of age, gender, race, or region, aval is for the time (days) to censor/relapse, and cnsr is for the status of censored (=0) or relapse (=1).

- SAS codes for testing the primary null hypotheses that the distribution of the time to first relapse for each of the cariprazine 4.5 mg/d and 3.0 mg/d treatment groups are not different from that for the placebo treatment group using log-rank test

```
proc lifetest data=adtte atrisk plots=survival(f atrisk=0 to 200 by
10 );
  time aval*cnsr(0);
  strata trt02p/test=logrank diff=control('Placebo');
  ods output ProductLimitEstimates=outests1 HomTests=test;
run;
```

- SAS codes for estimating the hazard ratio and 95% CIs based on the Cox proportional hazards model

```
proc phreg data=adtte;
  class trt02p(ref="Placebo");
  model aval*cnsr(0)=trt02p/rl=wald;
run;
```

- SAS codes for subgroup analyses

```
proc lifetest data=adtte atrisk plots=survival(f atrisk=0 to 200 by
10 );
  by subgroup;
  time aval*cnsr(0);
  strata trt02p/test=logrank diff=control('Placebo');
run;

proc phreg data=adtte;
  by subgroup;
  class trt02p(ref="Placebo");
  model aval*cnsr(0)=trt02p/rl=wald;
run;
```

APPENDIX II

DETAILS ON TWO SENSITIVITY ANALYSES MODELS AND SAS CODES TO EVALUATE THE POSSIBLE VIOLATION OF THE NONINFORMATIVE CENSORING ASSUMPTIONS

Two sensitivity analyses will be performed to assess the robustness of the primary analysis results to the possible violation of the noninformative censoring assumption. Both methods were used in maintenance supplemental New Drug Application (sNDA) filing based on single study RGH-MD-06 according to the discussion with the agency. One is delta-adjusted imputation method, which specifies that the hazard of having an event for subjects who discontinued before the time point is increased relative to the hazard for subjects who continued beyond the time point for the experimental treatment group. The delta-adjustment will be gradually increased from zero until reaching the tipping point when the statistical significance of the primary efficacy endpoint is overturned, and the plausibility of the magnitude of delta-adjustment needed for reaching the tipping point will be subject to clinical scrutiny. The second sensitivity analysis is based on the reference-based imputation method which specifies that the hazard for subjects in cariprazine arm who discontinued lies between the hazard for cariprazine subjects who continued and the hazard for the subjects in the placebo arm.

Two sets of sensitivity analyses were expressed below in the form of hazard rate function to illustrate the difference (Lu 2015). Suppose $h_0(t)$ and $h_1(t)$ are the hazard rate functions for placebo arm and treatment arm respectively. Under the non-informative censoring, one has $h_1(t) = h_0(t)e^\beta$, where β is the log hazard ratio characterizing the treatment effect. Under the informative censoring, hazard ratio function for two models are expressed as following,

- Before loss to follow up: $h_1(t) = h_0(t)e^\beta$
- After loss to follow up:
 - Reference-based method: $h_1(t) = h_0(t)e^{(1-\varphi)\beta}$, where $\varphi \in [0,1]$ is the sensitivity parameter
 - Delta-adjusted method: $h_1(t) = h_0(t)e^{\delta+\beta}$

Here, $\delta = -\varphi\beta$ implies the same underlying treatment effect. However, β will be estimated from the data, φ and δ should be prespecified. For reference based method, φ can take 1 as the maximum, which implies the extreme of change of $h_1(t)$ after the loss to follow up will be the same as the hazard for relapse for placebo-treated patients, ie the change will be in a clinical meaningful range. The selected sensitivity parameter φ will be 0, 0.2, 0.4, 0.6, 0.8 and 1 for this study for reference -based method. The selected δ in the delta-adjusted method will vary in steps of 0.1 or 0.2 till reaching tipping point when the statistical significance of the primary efficacy endpoint is overturned.

[figure not shown]
A multiple imputation approach will be used to implement the sensitivity analyses, which involves three periods.

[figure not shown]
1. The missing time to event are imputed m times to generate 50 complete datasets
2. The 50 complete datasets are analyzed using log rank test and cox model
3. The results from the 50 completer datasets are combined using Rubin's rule.

[figure not shown]
For the imputing stage, the latent event time will be imputed between censoring and planned follow up for subjects who prematurely discontinued. The baseline hazard function will be estimated using piecewise exponential approximation, and parameter β will be estimated from the data, which can be obtained using Gibbs sampling using the Bayes statement of the SAS PHREG procedure. Censored event times will be imputed for early withdrawals by inverting the conditional survivor function.

[figure not shown]
Texts below provide SAS codes to implement the multiple imputation, mainly based on the SAS codes for implementing the reference-based imputation method ([Lu 2015](#)).

[figure not shown]

[figure not shown]

[figure not shown]

[figure not shown]

[figure not shown]

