8.8 Early Discontinuation of Subjects

Patients may discontinue from the study at any time for any reason. Discontinuation is permanent; once a patient is discontinued, he/she shall not be allowed to enroll again.

Patients can be prematurely discontinued for one of the following reasons:

- AE

- Noncompliance with protocol
- Noncompliance with IP dosing regimen
- Withdrawal of consent (a clear reason must be documented when possible)
- Lost to follow-up (every effort must be made to contact the patient; a certified/traceable letter must be sent)
- Study terminated by sponsor
- Site terminated by sponsor
- Pregnancy
- Other reasons

Notification of early patient discontinuation from the study and the reason for discontinuation will be clearly documented on the appropriate eCRF page. Patients who take IP during the study (OL treatment period or the DB treatment period) and who prematurely discontinue from the study, regardless of cause, should be seen for a final assessment. A final assessment will be defined as completion of the evaluations scheduled for Visit 26/ET. If the patient discontinues after IP is taken, the patient is also expected to return for the SFU Visits (Visit 27 and Visit 28) 2 weeks and 4 weeks after completion of the ET visit.

At a minimum, collect the following information when a patient discontinues:

1. The reason the patient discontinued;
2. The date of the last dose of IP from the trial;
3. The date of the last assessment and/or contact. A follow-up contact (telephone or visit) will be arranged as appropriate;
4. (S)AEs;
5. Compliance with the IP administration as specified in this protocol;
6. Final Assessments: Unless there is withdrawal of consent, every effort should be made to ensure that all procedures and evaluations scheduled for Visit 26/ET and subsequently Visit 27 and Visit 28 (SFU Visits) are performed ([Table 2](#), Schedule of Visits and Procedures).

7. Retrieve IP from the patient.

For all patients who discontinue as a result of being lost to follow-up, a determination must be noted in the eCRF as to whether the loss is related to an acute exacerbation of schizophrenia.

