4.0 INTRODUCTION

This statistical analysis plan (SAP) describes the methodology that will be used to summarize the statistical analyses of the efficacy and safety data for the original protocol of Study RGH-MD-24 (version dated 28 June 2017) and its most recent amendment #4 dated 17 December 2019. On 14 DEC 2020, FDA provided Type C Written Response in which they agreed to release Allergan of the postmarketing requirement (PMR 2947-9) to conduct Study RGH-MD-24, based on new information obtained since initial Vraylar approval in SEP 2015. Study RGH-MD-24 was thus early terminated. The analyses for abbreviated CSR are specified in [Appendix IV](#).

Study RGH-MD-24 is a Phase 3B, multicenter, multinational, double-blind (DB) placebo-controlled, randomized-withdrawal study evaluating the efficacy, safety, and tolerability of cariprazine in a dose-reduction paradigm in the prevention of relapse in patients with schizophrenia. The key inclusion criteria are listed below: male or female 18 to 64 years of age, inclusive; meeting DSM-5 criteria for schizophrenia, whose current psychotic episode is < 4 weeks in duration at Visit 1; and having a Positive and Negative Syndrome Scale (PANSS) total score ≥ 70 and ≤ 120 at Visits 1 and 2, and a rating of at least 4 (moderate) on at least 2 of the following 4 PANSS positive symptoms; P1: delusions; P2: conceptual disorganization; P3: hallucinatory behavior, and P6: suspiciousness/persecution at Visits 1 and 2.

The length of this study will be up to 49 weeks, including a screening period of up to 7 days, followed by an up-to-18-week open-label treatment period (OLTP), and a 26-week double-blind treatment period (DBTP) and a 4-week safety follow-up (SFU) period. The details could be found in the protocol Section 3.

Screening/Washout Period: Patients meeting Diagnostic and Statistical Manual of Mental Disorders, Fifth Edition (DSM-5) criteria for schizophrenia will undergo a screening/washout period up to 7 days, during which consent, assessment of eligibility, and withdrawal of prior psychiatric and prohibited medications will occur. Patients may be hospitalized during initiation of the study. This hospitalization can be for up to 14 days during the screening and OLTP (with the end of hospitalization no later than Day 8 of the OLTP).

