10.1 PRIMARY EFFICACY PARAMETER

The primary efficacy parameter is the time to first relapse during the DBTP, defined as the number of days from the randomization date to the first relapse date. Relapse during the DBTP will be defined as the occurrence of any of the following:

- Increase in PANSS total score by $\geq 30\%$ for patients who had a PANSS total score of ≥ 50 at Randomization/Visit 13 (Week 18) or a ≥ 10 -point increase in PANSS total score for patients who had a PANSS total score < 50 at Randomization/Visit 13 (Week 18)
- Increase in CGI-S score by 2 or more points relative to Randomization/Visit 13 (Week 18)
- Score of > 4 on 1 or more of the following 7 PANSS items: P1: delusions; P2: conceptual disorganization; P3: hallucinatory behavior; P6: suspiciousness/persecution; P7: hostility; G8: uncooperativeness; G14: poor impulse control
- Deliberate self-injury or aggressive/violent behavior

- Initiation of treatment with a mood stabilizer, antidepressant, antipsychotic agent, or with a benzodiazepine that exceeds the protocol-specified allowance or duration (ie, more than 2 mg/d of lorazepam equivalent or for more than 3 consecutive days) to treat worsening symptoms of schizophrenia or any other psychiatric disorder as judged by the clinical impression of the investigator
- Psychiatric hospitalization due to worsening of the patient's underlying condition
- Exacerbation of psychiatric illness as judged by clinical impression of the investigator (e.g., clinically significant agitation, suicidal or homicidal ideations)

Patients who did not meet the above relapse criteria will be censored at the time of completion or discontinuation from the study.

To test the primary null hypotheses that the distribution of the time to first relapse for each of the cariprazine 4.5 mg/d and 3.0 mg/d treatment groups are not different from that for the placebo treatment group, the log-rank test is used to compare the time to relapse between each cariprazine group and placebo group for the DB ITT population. Estimates of the hazard ratio and 95% CIs will be based on the Cox proportional hazards model with treatment group as explanatory variable. The Kaplan-Meier estimates for the cumulative distribution of the relapse rate for each treatment group will be provided.

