The fixed-sequence testing procedure will be used for multiple comparisons to control the family-wise Type I error rate at a 0.05 level. The comparison of cariprazine 4.5 mg/d versus placebo for the primary endpoint will be tested first at a 0.05 significance level using the log rank test; the comparison of cariprazine 3.0 mg/d versus placebo will be tested only when the test for cariprazine 4.5 mg/d versus placebo is significant at 0.05 level.

Two sensitivity analyses will be performed to assess the robustness of the primary analysis results to the possible violation of the noninformative censoring assumption. The first sensitivity analysis is delta-adjusted imputation method ([Zhao 2014](#)). The delta-adjusted sensitivity analysis specifies that the hazard of having an event for subjects who discontinued before the timepoint is multiplicatively increased relative to the hazard for subjects who continued beyond the timepoint for the cariprazine treatment group. The second sensitivity analysis is based on the reference-based imputation method ([Lu 2015](#)). The reference-based sensitivity analyses use a sensitivity parameter to characterize the gradual deviation from the noninformative censoring underlying the primary analyses toward the informative censoring, which assumes that the hazard of relapse for cariprazine-treated patients who discontinued is the same as the hazard for relapse for placebo-treated patients. A multiple imputation approach will be used to implement the sensitivity analyses. Details for two sensitivity analyses including SAS codes were provided in [Appendix II](#).

The analysis for the primary efficacy parameter will be performed within each category of the following:

- Age group (< 55 years, \geq 55 years)
- Sex (male, female)
- Race (white, all other races)
- Region (US, Non-US)

SAS codes for planned analyses of the primary efficacy variable were provided in [Appendix I](#) and [Appendix II](#).

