APPENDIX IV ANALYSES SPECIFIED FOR ABBREVIATED CSR

On 14 DEC 2020, FDA provided Type C Written Response in which they agreed to release Allergan of the postmarketing requirement (PMR 2947-9) to conduct Study RGH-MD-24, based on new information obtained since initial Vraylar approval in SEP 2015. Study RGH-MD-24 was thus early terminated. The analyses for the abbreviated CSR are the subset of analyses specified in the SAP and listed below. The details are provided in the corresponding SAP sections.

Patient disposition and analysis populations

- Summary of screen failure patients and the associated reasons for failure
- Summary of patient disposition during OLTP and DBTP respectively
- Summary of analysis populations

Demographics and other baseline characteristics

- Summary of demographic and other baseline characteristics, and baseline efficacy variables
- Summary of prior and concomitant medications

Efficacy analyses

- Primary efficacy analysis
- Analyses of change from baseline in the PANSS total score during OLTP and DBTP
- Analyses of change from baseline in BACS composite score

Extent of exposure

- Summary of exposure during OLTP, DBTP and entire study

Safety analyses

- Overall summary of AEs during OLTP, OL Safety Follow-up, DBTP, and DB Safety Follow-up
- Summary of TEAEs during OLTP, OL Safety Follow-up, DBTP, and DB Safety Follow-up

- Summary of treatment-related TEAEs during OLTP and DBTP
- Summary of TEAEs leading to premature discontinuation of IP during OLTP and DBTP
- Summary of ocular events during OLTP, OL Safety Follow-up, DBTP, and DB Safety Follow-up
- Summary of TESAEs during OLTP, OL Safety Follow-up, DBTP, and DB Safety Follow-up
- Summary of TESAEs of ocular events during OLTP and DBTP
- Summary of laboratory PCS during OLTP and DBTP
- Summary of CSSRS during OLTP and DBTP

The following listings will be provided for the abbreviated CSR

- Patients with TEAEs leading to premature discontinuation of IP
- AEs for patients with TEAEs leading to premature discontinuation of IP
- Patients with ocular events
- AEs for patients with ocular events
- Patients who died
- AEs for patients who died
- Patients with SAEs
- Patients with laboratory PCS during OLTP and DBTP
- Patients who meet potential Hy's law criteria during OLTP and DBTP
- Patients with suicidal ideation or behavior
- Patient disposition
- Patients who discontinued OLTP or DBTP
- Patients with protocol deviations

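### If run as worded, the informative-censoring sensitivity analyses would also apply their hazard shift to cariprazine patients stopped only because the sponsor closed the study or site

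*SAP*

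**What the plan says.** **Scope of the imputation.** SAP Appendix II states that "the latent event time will be imputed between censoring and planned follow up for subjects who prematurely discontinued". It adds: "Censored event times will be imputed for early withdrawals by inverting the conditional survivor function". Neither sentence separates patients by reason for stopping. The hazard formulas in the same appendix are tied to loss to follow-up, which is a narrower term.

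**What counts as premature discontinuation.** Protocol 8.8 opens its list with "Patients can be prematurely discontinued for one of the following reasons". The list includes "Study terminated by sponsor" and, as a separate item, closure of a site by the sponsor.

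**What happened.** SAP Section 4.0 records: "Study RGH-MD-24 was thus early terminated". The reason given is release from a postmarketing requirement on the basis of information obtained since approval. Section 13.0 plans no interim analysis. The readable items of the Amendment 1 change list in Appendix V show no revision of Appendix II.

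**Primary analysis.** Under Section 10.1, patients who do not relapse are "censored at the time of completion or discontinuation from the study", whatever the reason.

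**Whether the sensitivity analyses are kept.** Section 10.1 says: "Two sensitivity analyses will be performed to assess the robustness of the primary analysis results". It points to Appendices I and II together for the code on the primary variable. Appendix IV restricts the abbreviated report to a listed subset, which names "Primary efficacy analysis" and refers to the relevant SAP sections for detail. Appendix I describes the primary efficacy analysis as the log-rank test, the Cox model and the subgroup analysis, without the imputation analyses.

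**The concern.** The two analyses ask how the result would look if cariprazine patients who dropped out went on to relapse at a higher rate than those who stayed. That question makes sense for withdrawal of consent, adverse events or loss to follow-up. It does not for a patient who was well and on treatment when the sponsor closed the study. On the documents' account, that stop followed a regulatory decision and carries no information about the patient's relapse risk.

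If such patients enter the imputation set, the stress test mixes two things: the dropout mechanism it was built to probe, and an administrative event that dilutes the contrast mechanically. The reported robustness would then depend partly on how many patients happened to be in follow-up at closure.

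**Working it through.** **1. Reproduce the planning figures.** Inputs from SAP Section 14.0: HR 0.50, placebo relapse 46% at Week 26, dropout 20% at Week 26, 115 patients per arm. With time in units of 26 weeks and exponential hazards:

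- placebo relapse hazard: −ln(0.54) = 0.616
- cariprazine relapse hazard: 0.5 × 0.616 = 0.308
- dropout hazard: −ln(0.80) = 0.223

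Expected events per arm = 115 × [λ/(λ+η)] × [1 − exp(−(λ+η))], where λ is the relapse hazard and η the dropout hazard:

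- placebo: 115 × 0.734 × (1 − 0.432) = 47.95
- each cariprazine arm: 115 × 0.580 × (1 − 0.588) = 27.49

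The three-arm total is 47.95 + 2 × 27.49 = 102.9, against 103 stated. A placebo comparison has 75.4 events, with Schoenfeld power 0.853 against 85% stated. The planning model is therefore understood and can carry the illustration.

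**2. What the shift does at each setting.** Under the reference-based method, the HR against placebo after discontinuation is exp[(1 − φ)β], where φ is the sensitivity parameter and β the log hazard ratio. With exp(β) = 0.50 this is 0.50^(1−φ):

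| φ | 0 | 0.2 | 0.4 | 0.6 | 0.8 | 1 |
|---|---|---|---|---|---|---|
| HR after discontinuation | 0.50 | 0.57 | 0.66 | 0.76 | 0.87 | 1.00 |

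Appendix II gives the equivalence δ = −φβ, so φ = 1 corresponds to δ = 0.693 here. At φ = 0 or δ = 0 nobody is shifted. Above 0, every imputed cariprazine patient is pulled towards the placebo hazard (or beyond it, for large δ), and a wider imputation set means a larger pull.

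**3. Effect of scope at φ = 1.** This is a simulation with 300,000 patients per arm under the planning hazards. A fraction of patients is assigned an administrative stop, uniform over the 26 weeks and unrelated to outcome. That fraction is an assumption, because the documents do not give it.

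| Assigned an administrative stop | Actually censored by it | HR, ordinary censoring | HR, dropouts imputed | HR, dropouts and terminated imputed |
|---|---|---|---|---|
| 0% | 0% | 0.498 | 0.545 | 0.542 |
| 10% | 7.2% | 0.499 | 0.544 | 0.562 |
| 20% | 14.6% | 0.502 | 0.548 | 0.586 |
| 30% | 21.7% | 0.500 | 0.546 | 0.598 |
| 50% | 36.3% | 0.501 | 0.547 | 0.639 |

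The two imputed columns in the first row describe the same rule, so their gap of 0.003 indicates the simulation noise. A separate simulation with uniform accrual and closure at the end of accrual (400,000 per arm) gave 0.583 at 14.5% and 0.638 at 36.3%, with 0.546 to 0.548 for dropouts only. The two agree.

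**4. What the shares imply.** With uniform accrual up to closure, the fraction randomized in the last 26 weeks is 26 divided by the accrual window in weeks. A 20% fraction needs 26/0.20 = 130 weeks, and a 50% fraction needs 26/0.50 = 52 weeks. The documents give no randomization dates, so neither can be confirmed.

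**The case against.** **The analyses may not be run.** Appendix IV does not name them, and Appendix I's description of the primary efficacy analysis leaves them out. That is the more direct reading, and it stands as a reason to state the point conditionally. It does not settle the matter. Section 10.1 commits to both analyses under the primary parameter and cites Appendix II for code. Appendix IV does not name the subgroup analyses either, although Appendix I counts them as part of the primary efficacy analysis.

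**The code may already filter by reason.** The imputation code does not appear in the text reviewed, so a filter cannot be ruled out. The loss-to-follow-up wording beside the formulas would also fit a narrower set. This stands too, but the prose rule is the broadest of the three wordings and contains no such limit.

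**It is only a graded stress test.** This is correct. A reader might infer that every cariprazine patient in follow-up at closure is assigned the placebo hazard. The documents do not say that: the reference-based parameter runs from 0 to 1 in steps of 0.2, delta starts at 0, and the placebo hazard applies only at φ = 1. Nor does the plan declare termination informative in the primary analysis, which simply censors.

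**The effect could be negligible.** The number stopped is unknown, and the documents do not say whether double-blind patients were withdrawn at closure or allowed to finish. A reader might extend the illustration to HRs near 0.7. With uniform accrual that would need about 70% to 90% of patients randomized in the final 26 weeks, that is, accrual windows of about 37 to 29 weeks, which nothing in the documents supports.

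**Conclusion.** The point holds conditionally, and it is minor. If the two sensitivity analyses are run as Appendix II words them, cariprazine patients stopped by study or site closure receive a hazard shift meant for informative dropout. The HR then moves further towards 1 whenever φ or δ exceeds 0. If the primary result is significant, the tipping point is reached sooner for a reason unrelated to the drug. The primary log-rank and Cox results do not change. The error runs against cariprazine, so it cannot create a false positive.

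The size is illustrative only. At φ = 1, the HR is about 0.55 with dropouts alone imputed, about 0.58 (0.583 and 0.586 in the two simulations) with about 15% administratively censored, and about 0.64 with 36%. This rests on the planning HR of 0.50, exponential relapse and dropout, termination unrelated to outcome, and assumed shares. The conclusion that the plan will in fact treat termination as informative goes further than the documents allow, because it is unresolved whether these analyses are kept and the code cannot be seen.

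**What to change.** 1. In Appendix II, define the imputation set once, in place of three different terms. Apply the delta or reference-based shift only to discontinuations other than study or site termination by the sponsor. Leave those patients censored at termination, or impute them with δ = 0 (φ = 0).
2. In Appendix IV, state whether the two sensitivity analyses are part of the abbreviated report, so that Appendix I and Section 10.1 no longer point in different directions.
3. If they are kept, report by arm how many patients were censored by termination.

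The cost is a sentence in each appendix, one filter in the code and one count. The discontinuation reason is already collected on the eCRF (Protocol 8.8; SAP Section 7.1).
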